6.7. Intervention after completion of Part A and Part B

Following the end of treatment at Week 52 or early withdrawal from the study, the participant will return to standard of care for SLE as determined by the investigator. Eligible participants who complete Part B (Section 6.7.1.1 and Section 6.7.1.2) may be enrolled into the optional access extension phase of the study from Week 52.

6.7.1. Optional Access Extension Phase

Access extension is an optional extension phase for 200908 to provide a mechanism for continued access to belimumab SC from Week 52 exclusively for eligible participants

(Section 6.7.1.1 and Section 6.7.1.2). The duration of this optional access extension phase depends on the age of participants when they are enrolled into the access extension phase and whether the circumstances leading to their eligibility change at any time (Section 6.7.1.3).

6.7.1.1. Optional Access Extension Phase Process

If per investigator's judgement a participant meets the eligibility criteria to enroll into the Optional Access Extension Phase, the Medical Monitor should be notified prior to enrolling any participant. The Investigator would be required to submit information related to their eligibility (see SRM for details), as determined by the specific inclusion and exclusion criteria (Section 6.7.1.2 and Section 6.7.1.3). Eligibility information will be reviewed by the Medical Monitor and enrollment into the Optional Access Extension Phase can only proceed following Medical Monitor approval.

6.7.1.2. Optional Access Extension Phase Inclusion Criteria

1. Male or female participants who complete Week 52 visit of the 200908 study.
2. Age <18 years at completion of Week 52.
3. Documented evidence of clinical benefit in 200908 study per investigator's judgement.
4. Able to comply with clinic visits and required assessments.
5. Intravenous (IV) Benlysta not currently licensed for the pediatric use in the participant's country; **OR** documented evidence of the rationale for IV Benlysta not being suitable for this participant requiring continued treatment with belimumab SC (including but not limited to: medical reasons, significant logistical challenges, or other legitimate reasons [discuss with medical monitor]).
6. Participant eligibility agreed with the Medical Monitor prior to enrolling the participant into the optional access extension phase.
7. Participant signs and dates a written age appropriate assent form specific for the access extension phase (in accordance with applicable regulations) and the parent or legal guardian (or emancipated minor) that has the ability to understand the requirements of the study, provides written informed consent specific to the access extension.

6.7.1.3. Optional Access Extension Phase Exclusion Criteria

1. Female participant has positive urine pregnancy test at Week 52 visit.
2. Female participant wishes to become pregnant at or within 4 months of Week 52 visit.
3. Participant has experienced any change in his/her medical history that, per the investigator's judgement, continued administration of belimumab therapy would be contraindicated.
4. Participant received a live vaccine within 30 days prior to Week 52

6.7.1.4. Optional Access Extension Phase Withdrawal Criteria

A participant may be withdrawn from the optional access extension phase by the investigator and/or Sponsor for reasons including but not limited to:

1. Participant reaches the age of 18 years.
2. Depending on the condition the participant was eligible for the optional access extension phase:
 - a. Belimumab SC (or IV) becomes licensed and commercially available for pediatric use in the participant's country.
 - b. The reason for which IV Benlysta was not suitable for this participant is no longer valid.
3. Participant becomes pregnant.
4. Participant receives prohibited therapy (See Section [6.5.2](#)).
5. Participant experiences unacceptable toxicity per investigator's judgement.
6. Participant participates in another interventional clinical trial.
7. Three Consecutive belimumab injections (see Section [6.4.2](#)) or consecutive clinic visits (see Section [8.5](#)) are missed.
8. Participant is no longer experiencing clinical benefit from belimumab per the documented medical judgement of the investigator.
9. Participant develops new or worsening of existing medical condition for which, in the opinion of the investigator or medical monitor, the risk of continued administration of belimumab outweighs clinical benefit to the participant; including liver chemistry stopping criteria (see Section [7.1.2](#)) and/or IgG stopping criteria (see Section [7.1.1](#)).
10. Sponsor becomes aware of new safety data that would preclude continued administration of SC belimumab.
11. It is the wish of the participant (or their legally acceptable representative) to withdraw for any reason.

Withdrawal from the optional access extension phase results in discontinued access to belimumab SC.

6.7.1.5. Optional Access Extension Phase Study Assessments and Procedures

- Study procedures and their timing during the optional access extension phase are summarized in the SoA (see Section [1.3.4](#)).
- Visit frequency in the access extension is every 12 weeks (\pm 7 days) after Week 52 and for the entire duration of the optional access extension phase.
- Body weight should be checked at the beginning of each clinic visit and should be noted in the Investigators source documents. As the dosing frequency may change due to changes in participant's body weight, Section [6.6](#) should be followed for any

dose modifications. Any changes in body weight that lead to a change in dosing frequency should be noted and requested in the IWRS system (see SRM for details).

- No efficacy assessments are required during the optional access extension phase. The investigator will use their judgement to determine and continue to evaluate the clinical benefit from belimumab SC and participants who are no longer experiencing clinical benefit will be withdrawn.
- Although routine safety laboratory monitoring is not required during the optional access extension phase, local laboratory assessments can be performed as part of the participant's routine evaluation or can be triggered by the investigator should a safety signal warrant further investigation per the investigator's judgement. Any abnormal results will be noted in the Investigator's source documents. The GSK Medical Monitor should be informed of any result that meets the safety stopping criteria (e.g. Liver Stopping Criteria in Section 7.1.2 and Grade 4 IgG level Section 7.1.1).
- Serious adverse event (SAE) definition and reporting during the optional access extension phase will follow the guidance in Section 8.9. During the optional access extension phase, SAEs will be reported to GSK via paper CRF only (see Section 10.3.4).
- For females of childbearing potential: urine pregnancy tests will be provided by sites at the scheduled visits in SOA (Section 1.3). Participants will be required to perform a urine pregnancy test every 4 weeks throughout the treatment period (1 onsite and 2 at home). Home urine pregnancy tests will also be provided for the 8-week and 16-week follow-up period. The results of urine pregnancy tests conducted at home will be recorded in the subject diary cards and stored as part of the investigator's source documents. Only positive pregnancy test results will be reported to GSK during the optional access extension phase and will follow the guidance in Section 8.9.5.
- Participants and caregivers will be provided with a subject diary card (refer to SRM for details). Participants must complete the subject diary card and bring it with them to each site visit. Compliance for all dosing, pregnancy testing and autoinjector malfunctions will be assessed and reviewed by the Investigator or site staff, with the participant/caregiver at each site visit. For any dosing or pregnancy testing conducted at the investigative site, participants or caregivers will complete the subject diary card. Results will not be reported and the completed subject diary card will be stored in the Investigator's source documents.
- A record of the number of belimumab autoinjectors dispensed to and taken by each participant and of unused autoinjectors returned by each participant must be maintained and reconciled with study treatment and compliance records. Participants and caregivers are required to return all used and unused autoinjector devices to the site, for their local disposal and destruction. All used autoinjectors should be placed in a sharps container and returned to site (see SRM for details). Any returned malfunctioning autoinjectors will be marked to distinguish them from the used autoinjectors (see SRM for details).
- Medical device incidents and malfunction reporting during the optional access extension phase will follow the guidance in Section 8.9.6 and Section 8.9.7.

- If participants withdraw from treatment at any time during the optional access extension phase, an early withdrawal (EW) visit should be completed. Additionally, 8 and 16-week follow-up visits are required via phone call to collect SAEs, and the results of home urine pregnancy test (if applicable) for female participants.

6.7.1.6. Optional Access Extension Phase Statistical Analyses and Reporting

- There are no formal statistical analyses being performed in the optional access extension phase.
- Summary of SAEs, pregnancies and medical device incidents reported in the safety database during the optional access extension phase will be provided in a synoptic clinical study report after conclusion of the optional access extension phase.

7. DISCONTINUATION OF STUDY INTERVENTION AND PARTICIPANT DISCONTINUATION/WITHDRAWAL

7.1. Discontinuation of Study Intervention

If study intervention is permanently discontinued, the participant will complete the early withdrawal and follow-up visits as described in Section 8.5 and Section 1.3 (SoA) and will be withdrawn from the study.

Participants may be withdrawn from study agent and from the study if at any time:

- It is the wish of the participant (or their legally acceptable representative) for any reason.
- The investigator judges it necessary due to medical reasons.
- Consecutive belimumab injections (see Section 6.4.2) or consecutive clinic visits (see Section 8.5) are missed.

Furthermore, participants will be withdrawn from study agent and subsequently withdrawn from the study if at any time they:

- Become pregnant.
- Receive prohibited therapy (See Section 6.5.2)
- Experience unacceptable toxicity
- Participate in another interventional clinical trial
- Trigger liver chemistry stopping criteria (see Section 7.1.2) and/or IgG stopping criteria (see Section 7.1.1).

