7.1.1. IgG Stopping Criteria

Any participant who has a Grade 4 IgG level, by the protocol defined Adverse Event and Laboratory Value Severity Grade Scale (see [Appendix 2](#), Section 10.2.1), will have dosing with study agent withheld, and the appropriateness to continue study treatment must be discussed with the Medical Monitor before the next dose. Any participant who has a Grade 4 IgG level associated with a severe or serious infection will have study agent discontinued and should complete the follow-up assessments as described in the SoA (Section 1.3).

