7.1.2. Liver Chemistry Stopping Criteria

Liver chemistry stopping and increased monitoring criteria have been designed to assure participant safety and evaluate liver event etiology.

[figure not shown]
Discontinuation of study treatment is required when:

- a participant meets one of the conditions outlined in [Algorithm A](#) or [Algorithm B](#)

OR

- when in the presence of abnormal liver chemistries not meeting protocol-specified stopping rules, the investigator believes study treatment discontinuation is in the best interest of the participant.

[figure not shown]
Algorithm A: Phase III-IV Liver Chemistry Stopping and Increased Monitoring Algorithm

Abbreviations: ALT = alanine transaminase; bili = bilirubin; INR = international normalized ratio; SAE = serious adverse event; ULN = upper limit of normal.

See [Appendix 5](#) for liver safety required actions and follow-up assessments.

Algorithm B: Phase III-IV Liver Chemistry Increased Monitoring Algorithm with Continued Therapy for ALT $\geq 3 \times$ ULN but $< 8 \times$ ULN

Abbreviations: ALT = alanine transaminase; bili = bilirubin; INR = international normalized ratio; SAE = serious adverse event; ULN = upper limit of normal.

See [Appendix 5](#) for liver safety required actions and follow-up assessments.

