- Any female participant who becomes pregnant while participating will discontinue study intervention and be withdrawn from the study.
- Investigator will collect pregnancy information on any female participant, who becomes pregnant while participating in this study.
- Information will be recorded on the appropriate form and submitted to GSK within 24 hours of learning of a participant's pregnancy.
- Participant will be followed to determine the outcome of the pregnancy. The investigator will collect follow-up information on participant and neonate, which will be forwarded to GSK. Generally, follow-up will not be required for longer than 6 to 8 weeks beyond the estimated delivery date.
- Any termination of pregnancy will be reported, regardless of fetal status (presence or absence of anomalies) or indication for procedure.
- While pregnancy itself is not considered to be an AE or SAE, any pregnancy complication or elective termination of a pregnancy for a medical reason will be reported as an AE or SAE.
- A spontaneous abortion is always considered to be an SAE and will be reported as such.
- Any SAE occurring as a result of a post-study pregnancy which is considered reasonably related to the study intervention by the investigator, will be reported to GSK as described in [Appendix 3](#). While the investigator is not obligated to actively seek this information in former study participants, he or she may learn of an SAE through spontaneous reporting.

10.5. Appendix 5 Liver Safety: Required Actions and Follow-up Assessments and Study Intervention Restart Guidelines

Phase III-IV liver chemistry stopping and increased monitoring criteria have been designed to assure participant safety and evaluate liver event etiology

Phase III-IV liver chemistry stopping criteria and required follow-up assessments

Liver Chemistry Stopping Criteria	
ALT-absolute	ALT \geq 8xULN
ALT Increase	ALT \geq 5xULN but <8 xULN persists for ≥ 2 weeks ALT \geq 3xULN but <5 xULN persists for ≥ 4 weeks
Bilirubin^{1, 2}	ALT \geq 3xULN and bilirubin \geq 2xULN ($>35\%$ direct bilirubin)
INR²	ALT \geq 3xULN and INR >1.5
Cannot Monitor	ALT \geq 5xULN but <8 xULN and cannot be monitored weekly for ≥ 2 weeks ALT \geq 3xULN but <5 xULN and cannot be monitored weekly for ≥ 4 weeks
Symptomatic³	ALT \geq 3xULN associated with symptoms (new or worsening) believed to be related to liver injury or hypersensitivity
Required Actions and Follow-up Assessments	
Actions	Follow-Up Assessments

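### The protocol gives conflicting consequences for Grade 4 IgG without a severe or serious infection, and the extension lists stops that are mandatory elsewhere under permissive wording

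*Protocol*

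**What the plan says.** **IgG.** Protocol Section 7.1 has two lists. The first gives reasons for which participants may be withdrawn. The second opens with "Furthermore, participants will be withdrawn from study agent and subsequently withdrawn from the study if at any time they" and includes "Trigger liver chemistry stopping criteria (see Section 7.1.2) and/or IgG stopping criteria (see Section 7.1.1".

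Section 7.1.1, headed IgG Stopping Criteria, has two tiers. A participant with Grade 4 IgG "will have dosing with study agent withheld, and the appropriateness to continue study treatment must be discussed with the Medical Monitor". If the Grade 4 level is associated with a severe or serious infection, study agent is discontinued. The risk table in Section 2.3.1 repeats both tiers with the threshold written out (below 250 mg/dL, which is Grade 4 in Appendix 2).

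Section 6.7.1.5, on the optional access extension, says: "The GSK Medical Monitor should be informed of any result that meets the safety stopping criteria". It gives two examples: the liver criteria of 7.1.2 and a Grade 4 IgG level under 7.1.1.

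**Extension withdrawals.** Section 6.7.1.4 opens: "A participant may be withdrawn from the optional access extension phase by the investigator and/or Sponsor for reasons including but not limited to". Item 3 is pregnancy and item 4 prohibited therapy. Item 9 is a new or worsening condition for which, in the opinion of the investigator or Medical Monitor, risk outweighs benefit; it names the liver and IgG stopping criteria as included.

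Elsewhere the wording is mandatory. Section 7.1.2: "Discontinuation of study treatment is required when" the liver algorithms are met. Appendix 4: "Any female participant who becomes pregnant while participating will discontinue study intervention and be withdrawn from the study". Section 6.5.2 says belimumab will be discontinued and the participant withdrawn if prohibited therapy is started. Appendix 5 requires immediate discontinuation once a liver criterion is met, and Section 7.1.2.1 bars restart.

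**The concern.** A stopping rule should lead every reader to the same action. Two sets of passages do not.

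For Grade 4 IgG without a severe or serious infection, a site that takes Section 7.1 together with 6.7.1.5 would withdraw the child from treatment and study. A site that takes 7.1.1 or 2.3.1 would hold the dose, call the Medical Monitor and possibly resume.

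In the extension, a site that opens Section 6.7.1.4 finds pregnancy, prohibited therapy and the liver criteria listed as possible reasons for withdrawal, the last subject to opinion. A site that opens 6.5.2, 7.1, 7.1.2 or the appendices finds that the same events require a stop. At stake is consistent safety handling of children on treatment, and being able to say afterwards whether a given action was a protocol deviation.

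**Working it through.** No arithmetic applies and the plan states no figure to reproduce. The check is to set the passages side by side.

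**Step 1: IgG.** Section 7.1 sets no IgG threshold of its own; it points to 7.1.1. The outcome depends on which tier of 7.1.1 counts as the stopping criteria.

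| Situation | 7.1, if this situation is the trigger | 7.1.1 and 2.3.1 |
|---|---|---|
| Grade 4 IgG, no severe or serious infection | Withdrawn from agent and study | Dose withheld; continuation discussed with the Medical Monitor |
| Grade 4 IgG with severe or serious infection | Withdrawn from agent and study | Study agent discontinued |

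The second row agrees. The first conflicts unless Grade 4 alone is not a trigger. Two features point to its being one: the heading of 7.1.1 covers both tiers, and 6.7.1.5 cites Grade 4 IgG under 7.1.1, without infection, as an example of a result meeting the stopping criteria.

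**Step 2: extension withdrawals.** Each entry in the mandatory list of 7.1 is matched to 6.7.1.4.

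| Reason | 7.1 | Other mandatory text | 6.7.1.4 (lead-in *may*) |
|---|---|---|---|
| Pregnancy | *will* | Appendix 4 | Item 3 |
| Prohibited therapy | *will* | 6.5.2 | Item 4 |
| Unacceptable toxicity | *will* | – | Item 5, by investigator judgement |
| Another interventional trial | *will* | – | Item 6 |
| Liver criteria | *will* | 7.1.2, Appendix 5 | Item 9, by opinion |
| IgG criteria | *will* | Infection tier of 7.1.1 | Item 9, by opinion |

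Section 7.1 joins liver and IgG in one entry, so its mandatory list has five entries. All five reappear under the permissive lead-in of 6.7.1.4.

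**Step 3: does phase explain the difference?** Section 7.1 applies at any time, and 6.5.2, 7.1.2 and Appendices 4 and 5 carry no restriction to Parts A and B. Nothing says that 6.7.1.4 replaces them in the extension, and nothing in 6.7.1.4 says that they take precedence over it.

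**Step 4: is the lead-in consistent with the extension's own text?** No. Section 4.1 says extension participants *will* be withdrawn at age 18 or on pediatric licensing and availability, and refers to 6.7.1.4 for the full criteria, where these are items 1 and 2a under *may*. Section 6.7.1.5 says participants who no longer benefit *will* be withdrawn; that is item 8 under *may*.

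**The case against.** **IgG.** The sections can be read together. Section 7.1 refers to 7.1.1, so a site following the reference reaches the two-tier rule, and the tier that stops treatment agrees with 7.1. Section 6.7.1.5 only asks that the Medical Monitor be informed, which fits the discussion step. That reading is available, but the protocol does not state it, and the heading of 7.1.1 and the example in 6.7.1.5 point the other way. The ambiguity stands.

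**Extension.** The *may* lead-in can be read as introducing a list of reasons, since several items are mandatory elsewhere. The mandatory rules also still reach the extension. Section 6.7.1.5 sends positive pregnancy tests to 8.9.5, which leads to Appendix 4; item 9 cross-refers to 7.1.1 and 7.1.2. This is a fair answer to anyone inferring that 6.7.1.4 has replaced the mandatory stops: the documents do not show that. What remains is an unreconciled *will* against *may*.

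Four further inferences are tempting but unsupported:

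- *That 7.1.1 does no more than withhold dosing.* It mandates discontinuation when a severe or serious infection is present.
- *That the two IgG rules always give opposite outcomes.* The Medical Monitor discussion is compulsory before the next dose and may itself end treatment.
- *That the extension has no scheduled laboratory tests.* Urine pregnancy tests are required every 4 weeks, and Section 1.3.4 lists them as laboratory assessments. Liver chemistry and IgG are indeed unscheduled, but the protocol says so openly: "Although routine safety laboratory monitoring is not required during the optional access extension phase". Local testing is allowed. That is a disclosed design choice, not a contradiction.
- *That the primary PK results are affected.* No frequency is given. Exclusion 11 bars Grade 3 or worse laboratory abnormalities with no IgG exception, so screening IgG must be at least 400 mg/dL and would have to fall by more than 400 − 250 = 150 mg/dL to reach Grade 4. Dosing is interrupted under either reading, and one analyzed post-dose sample keeps a participant in the PK population.

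**Conclusion.** The point holds in two parts. The consequence of Grade 4 IgG without a severe or serious infection is contradictory across Sections 7.1, 7.1.1, 2.3.1 and 6.7.1.5. And 6.7.1.4 places pregnancy, prohibited therapy and the liver and IgG criteria under permissive wording, while 6.5.2, 7.1, 7.1.2 and Appendices 4 and 5 make the first two and the liver stop mandatory in every phase.

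The size is one of clarity, not of numbers. All five entries in the mandatory list of 7.1 are affected in the extension, and one IgG situation is affected throughout. No sample size, estimate or planned analysis changes, and Section 6.7.1.6 plans no formal analysis of the extension. Few cases may arise. The point still deserves correction, because these are safety stopping rules in children and the reader must guess which section governs.

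This rests on the protocol text alone. The Study Reference Manual is not available here and may say more, and the liver algorithm figures are not shown, although Appendix 5 gives their criteria in text. Which rule is clinically right is not judged here.

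**What to change.** 1. Reconcile Sections 7.1, 7.1.1, 2.3.1 and 6.7.1.5 so that Grade 4 IgG alone, and Grade 4 IgG with a severe or serious infection, each have one stated consequence, and so that the term for the stopping criteria covers the same situations wherever it is used.
2. In Section 6.7.1.4, separate mandatory from discretionary reasons, as Section 7.1 already does with its two lists. Give each reason the same status as in 6.5.2, 7.1, 7.1.2 and Appendices 4 and 5, or state why the extension differs. Align items 1, 2a and 8 with Sections 4.1 and 6.7.1.5 at the same time.

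The sponsor decides which rule applies in each case. The cost is amendment wording in the five sections named above (7.1, 7.1.1, 2.3.1, 6.7.1.5 and 6.7.1.4). Removing the contradictions needs no new test, visit or data collection, and no change to the SAP.
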